4. ANALYSIS SETS (POPULATIONS FOR ANALYSIS)

For purposes of analysis, the following populations are defined:

Population	Description
Enrolled	All participants who sign the Informed Consent Document.
All Randomized	All participants, including siblings and those meeting exclusion criterion 15, who were randomly assigned to Cohort 1 (initially fordadistrogene movaparvovec) or Cohort 2 (initially placebo).
Full Analysis Set (FAS)(through Week 52) ^a	All participants, excluding siblings and those meeting exclusion criterion 15, who were randomly assigned and received a single dose of IP on Day 1 (Year 1 Day 1). Participants will be analyzed according to the cohort to which they were randomized.
Safety Analysis Set (through Week 52)	All participants, including siblings and those meeting exclusion criterion 15, who were randomly assigned and received a single dose of IP on Day 1 (Year 1 Day 1). Participants will be analyzed according to the IP they actually received. Note: Per protocol amendment #6 and protocol amendment 12 (Section 5.2 and 10.12), participants in Cohort 2 who had already received IP (ie, placebo) at the time of implementation of the temporary enrolment and dosing pause, and who are retrospectively determined to meet exclusion criterion 15 upon approval of protocol amendment 6 will not be eligible for Year 2 IP (ie, fordadistrogene movaparvovec) administration and will be withdrawn from the study immediately upon determination of non-eligibility. These participants will be included in the Safety Analysis Set (through Week 52); however, they will contribute partial data.

^a Of note, per the PCD definition in protocol amendment 15, the primary analysis will occur after at least 90 FAS participants complete Day 360 (Visit 19) or discontinue from the study prior to Week 52 if they had received Year 1 IP at least one year prior to the data cutoff.

In addition, as a subset of participants had biopsy samples taken to assess mini-dystrophin levels, and a subset of participants had whole blood, urine and saliva samples taken to assess viral vector shedding kinetics, the following population is defined:

Population	Description
Viral Vector Shedding	For each matrix, all participants, including siblings and those meeting exclusion criterion 15, who were randomly assigned, received a single dose of fordadistrogene movaparvovec on Day 1 (Year 1 Day 1), and who had at least two post-Baseline measurements within the first 7 days after fordadistrogene movaparvovec administration.

Data for all participants will be assessed to determine if participants meet the criteria for inclusion in each analysis population prior to unblinding and releasing the database and classifications will be documented per standard operating procedures.

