6.7. Safety Summaries and Analyses

All analyses will be performed for the Safety Analysis Set (through Week 52).

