6.7.1. Adverse Events

Incidence of TEAEs (all-causality and treatment-related) in the reporting period will be summarized by SOC, PT, and severity for fordadistrogene movaparvovec and placebo. Adverse events may be clustered to reflect medical concepts.

A summary of the TEAEs (all-causality and treatment-related) occurring during the reporting period will be tabulated by PT sorted by decreasing incidence for fordadistrogene movaparvovec and placebo. The most commonly reported TEAEs will be summarized using those PTs with high frequency (cutoff depends on the final frequency of TEAEs) for fordadistrogene movaparvovec-dosed participants in the safety analysis set.

Deaths and SAEs will be listed and incidence of SAEs(all causality and treatment-related) will be summarized by SOC and PT for fordadistrogene movaparvovec and placebo.

A summary of the SAEs (all-causality and treatment-related) occurring during the reporting period will be tabulated by PT sorted by decreasing incidence for fordadistrogene movaparvovec and placebo. The most commonly reported SAEs will be summarized using those PTs with high frequency (cutoff depends on the final frequency of serious TEAEs) for fordadistrogene movaparvovec-dosed participants in the safety analysis set.

For each participant who reported a TEAE (all-causality or onset treatment-related), the time (in days) to (date of onset of the event - date of dosing + 1) for that TEAE will be summarized by PT as continuous data. Participants with multiple TEAEs will be included multiple times in the summary statistics. Events that occur on the day of dosing will have a time of onset as day 1.

For each participant who reported a serious TEAE (all-causality or treatment-related), the time (in days) to onset (date of onset of the event - date of dosing + 1) for that serious TEAE will be summarized by PT as continuous data. Participants with multiple serious TEAEs will be included multiple times in the summary statistics. Events that occur on the day of dosing will have a time of onset as Day 1.

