Adverse events of interest will be summarized using incidence of all-causality AEs (by severity) and SAEs (across all severities). Several PTs would be combined as cluster terms, and incidence for both component PTs and cluster terms will be included. Cluster categories and PTs with “Peri infusion” will include AEs of interest with an onset in the first 2 weeks after dosing (Day 1 through Day 14) while “Late Onset” will include AEs of interest with an onset date after week 4 (Week 5 or later). The final list of AEs of interest will be maintained in a separate document and finalized before the database release.

Onset of AEs of interest (all-causality) will be summarized by intervals. The interval is defined as the number of weeks rounded to next highest integer from the fordadistrogene movaparvovec or placebo administration to the earliest of date of AE of interest or date of data cut-off (i.e., [end date – dosing date +1]/7 for weeks. The total duration of follow up for each participant is relative to death/study discontinuation/or data cut-off. For example, week 1 is for days 1-7 and week 2 is for days 8-14).

For each duration of follow-up interval, total number of AEs of interest that occur during an interval will contribute to the numerator of the percentage. Total count of AEs of interest that occur in the entire reporting period will contribute to the denominator of the percentage. Day 390 or one day prior to Year 2 dosing will be considered as having follow-up up to 52 weeks.

The AEs of interest for both cluster terms and the component PTs will be summarized by interval durations in weeks. For these AEs of interest cluster terms and the components PTs, duration of the adverse events will be summarized descriptively (N, mean, SD, median, Q1, Q3, minimum, and maximum). Participants with multiple AEs of interest will be included multiple times in the summary statistics.

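### The adverse-event comparison through Week 52 has no measure that allows for unequal follow-up, and the by-interval table divides by events instead of boys at risk

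*SAP*

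**What the plan says.** **Who is followed for less time.** The note to the Safety Analysis Set (SAP Section 4) concerns Cohort 2 boys who had already received placebo at the dosing pause and were later found to meet exclusion criterion 15. They cannot receive the Year 2 infusion and "will be withdrawn from the study immediately upon determination of non-eligibility. These participants will be included in the Safety Analysis Set (through Week 52"). The note adds that their data will be partial. No matching withdrawal is stated for Cohort 1. Separately, the footnote in Section 4 and the opening of Section 5 allow the primary analysis once at least 90 FAS participants have completed Day 360 or discontinued. About 99 are planned (Section 2.3).

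**How events are compared.** Section 6.7 uses one population: "All analyses will be performed for the Safety Analysis Set (through Week 52"). Section 6.7.1 gives the measure: "Incidence of TEAEs (all-causality and treatment-related) in the reporting period will be summarized by SOC, PT, and severity for fordadistrogene movaparvovec and placebo". SAEs are handled in the same way. Time to onset is summarised only among boys who had the event. Kaplan-Meier methods (Section 5.2.2) are used in this plan only for vector shedding (Section 6.3.8).

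**The by-interval table.** For AEs of interest, Section 6.7.1 counts weeks from dosing and defines each boy's follow-up as ending at death, discontinuation or data cut-off. The percentage does not use that follow-up: its numerator is the number of events in the interval, and "Total count of AEs of interest that occur in the entire reporting period will contribute to the denominator of the percentage".

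**The concern.** The safety objective in Section 2.2 is a comparison with placebo through Week 52. Simple incidence over a fixed year is a fair comparison when both arms are watched equally long. Here the SAP itself describes a group, in the placebo arm only, whose follow-up is cut short for an administrative reason, and it keeps that group in the analysis set. A boy who leaves early cannot report a later event but still counts as one participant. If enough boys are affected, placebo incidence of later or steadily accruing events comes out too low.

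The by-interval table is where a reader would look to see risk over time, for the events that the sponsor has singled out. The follow-up needed for a proper denominator is defined there and then left unused.

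**Working it through.** The SAP states no figure for the adverse-event comparison, so there is none to reproduce. Its power statement (Section 2.3.1) concerns the primary efficacy endpoint and plays no part here.

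**1. Effect of early withdrawal on crude placebo incidence**

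Inputs:
- 33 placebo boys with full follow-up: the approximate Cohort 2 size in Section 2.3. Criterion-15 boys are outside the FAS, so they are added on top. Siblings are ignored.
- k criterion-15 placebo boys, each followed for a fraction f of the year. Neither is in the SAP. Assumed ranges: k = 1 to 6 and f = 0.10 to 0.75.
- True one-year risk r = 30% and constant hazard, both assumed.
- The denominator is the whole Safety Analysis Set. This is inferred from Sections 6.7 and 6.7.1, which do not write it out.

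Expected crude incidence = [33r + k(1 − (1 − r)^f)] / (33 + k).

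For k = 6 and f = 0.10: 1 − 0.7^0.10 = 0.0350, so (9.9 + 6 × 0.0350)/39 = 10.11/39 = 25.9%.
For k = 1 and f = 0.75: 1 − 0.7^0.75 = 0.2347, so (9.9 + 0.2347)/34 = 29.8%.

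| k | f = 0.10 | f = 0.75 |
|---|---|---|
| 1 | 29.2% | 29.8% |
| 3 | 27.8% | 29.5% |
| 6 | 25.9% | 29.0% |

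The shortfall against 30% runs from 0.2 to 4.1 points. With equal true risk in the two arms, the active/placebo ratio is inflated by a factor of 0.30/0.298 = 1.006 to 0.30/0.259 = 1.16. Across true risks from 10% to 60%, the shortfall runs from 0.1 to 7.9 points. If all events fall in the first days after infusion, before anyone is withdrawn, it is nil.

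**2. Data-cut rule**

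99 − 90 = 9, so up to about nine FAS boys could have incomplete follow-up at the cut. They may be in either arm, so no direction is expected.

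**3. What the by-interval percentage measures**

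Hypothetical counts: 60 events of interest among 66 treated boys, 24 of them in Weeks 1–2; and 5 events among 33 placebo boys, 2 of them in Weeks 1–2.
- Denominator taken per arm: 24/60 = 40% and 2/5 = 40%. Events per boy are 24/66 = 0.36 and 2/33 = 0.06, a six-fold difference that the table does not show.
- Denominator pooled over arms: 24/65 = 37% and 2/65 = 3%, a twelve-fold contrast, because 2:1 allocation doubles the true six-fold one.

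The SAP does not say which denominator applies. Neither gives risk.

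**4. Which adjustment is suitable**

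A rate of boys with an event per person-year suits a constant hazard, but each boy receives a single Day 1 infusion. Suppose that all risk falls near Day 1, true risk is 30% in both arms, and six placebo boys leave at Week 10 in addition to 33 followed fully.
- Active: 0.3/0.7 = 0.43 per person-year.
- Placebo: 39 × 0.3 = 11.7 boys with an event. Time at risk is 33 × 0.7 + 6 × 0.7 × 10/52 = 23.1 + 0.81 = 23.91 person-years. The rate is 11.7/23.91 = 0.49.

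That is a false placebo excess of 14%, where crude incidence would be correct. A Kaplan-Meier estimate gives 30% in both arms here, and its expected value is also close to 30% in the constant-hazard case of step 1.

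**The case against.** Several points on the other side stand.

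- The criterion-15 group is closed and may be very small. The SAP discloses its partial data, and Section 6.6.2 summarises discontinuation and its reasons by arm. A reader might infer that placebo incidence is known to be biased by a material amount. The documents do not support that, since neither the number of boys nor their follow-up is given, and with one boy the effect is under one point at 30% risk.
- A reader might infer that the design hides harm. The direction is the reverse: a low placebo figure makes active look relatively worse.
- It would also be wrong to treat these boys as unobserved. They contribute data until withdrawal.
- The distribution of onset times is a legitimate description. Section 6.7.1 separately gives incidence of AEs of interest, including peri-infusion clusters limited to Days 1–14, so a large early difference in such events would be seen elsewhere.
- The late-onset clusters "will include AEs of interest with an onset date after week 4 (Week 5 or later"), and a reader might infer that events on Days 15–28 are lost. They are not. Nothing says that these labels must cover all of follow-up, and such events remain in the overall incidence tables and the weekly table.

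These points limit the size of the concern and leave two gaps. No planned output adjusts the adverse-event comparison for follow-up that the SAP itself calls partial, and the by-interval percentage cannot be read as risk under either denominator.

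**Conclusion.** The point holds as a modest and inexpensive improvement to the safety analysis. The by-interval part rests on the text alone: the denominator is events, so the percentage cannot compare risk between arms. The follow-up part rests on assumptions. With 1 to 6 affected placebo boys, a 30% one-year risk, constant hazard and the full Safety Analysis Set as denominator, crude placebo incidence would be about 0 to 4 points too low for events that accrue through the year. The true size is unknown, and peri-infusion events are barely affected. The data-cut rule may add incomplete follow-up in both arms, without an expected direction.

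**What to change.** In SAP Section 6.7.1:

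1. In the by-interval table for AEs of interest, report by arm the number of boys with an event in the interval over the number still in follow-up at its start, using the follow-up duration already defined there. The onset distribution may stay as an extra column, with its denominator stated as per arm or pooled.
2. For SAEs and AEs of interest, give Kaplan-Meier or cumulative incidence through Week 52 by arm beside crude n (%), and report follow-up time by arm. Do not rely on a constant-hazard person-year rate, for the reason shown in step 4 of the working.
3. Optionally, add one sensitivity table that excludes criterion-15 boys from both arms. Kaplan-Meier assumes that withdrawn boys would have had the same later risk as those who stayed, and this table avoids relying on that assumption for them.

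All of this uses dates of dosing, onset, discontinuation and cut-off that the planned analyses already need. It changes no analysis set and no efficacy analysis. The cost is SAP wording, some programming and a few more safety tables.

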3.3.4. Viral Vector Shedding Endpoints

Whole blood, saliva, and urine samples for viral vector shedding kinetics will be collected in approximately the first 45 treated participants (approximately 30 treated with fordadistrogene movaparvovec and approximately 15 treated with placebo). For each randomized participant, sample collection for a particular matrix (sample type) will be stopped when at least 2 consecutive negative results are observed in that matrix.

Viral vector levels (vector genomes /ml), measuring intact and fragmented copies, will be determined in whole blood, saliva and urine using qPCR analysis. Additionally, intact viral vector levels (vector genomes/mL) in saliva and urine samples will be measured as intact copies following treatment with Micrococcal Nuclease (MNase). Viral vector shedding results below the lower limit of quantification (BLQ) for each matrix are considered negative or “undetectable. [Section 6.3.8](#) describes the approach for handling results that are undetectable.

For each of the 5 viral vector level profiles, one without MNase treatment for whole blood, one without MNase for saliva, one with MNase for saliva, one without MNase for urine, and one with MNase for urine, the following endpoints will be determined:

- Peak viral vector levels (vg/ml) post fordadistrogene movaparvovec administration.

Defined as the largest detectable result collected prior to the first set of 2 consecutive negative results.

- Time in weeks to peak viral vector shedding post fordadistrogene movaparvovec administration.

Defined as the time in weeks from the date of fordadistrogene movaparvovec administration to the peak viral vector result defined above.

- Time in weeks to undetectable viral vector (time to clearance of viral vector) from date of fordadistrogene movaparvovec administration.

The first set of 2 consecutive negative results is identified and then time to undetectable viral vector is defined as the time in weeks from the date of fordadistrogene movaparvovec administration to the first of the 2 consecutive negative results identified. If at the time of analysis, the last result is positive or negative results have not been confirmed, the time is recorded at the last date on which a sample for the particular matrix occurs and will be marked as censored for the analysis, meaning the time to undetectable viral vector clearance is at least that value.

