6.3.8. Viral Vector Shedding

Samples collected for viral vector shedding are only assayed for Cohort 1 (initially fordadistrogene movaparvovec) participants.

Note that there may be participants for which sample collection may continue after 2 consecutive undetectable samples because notification to stop may be provided after the participant has had another scheduled visit where a sample was to be collected or a site may mistakenly collect a sample after receiving notification to stop sample collection.

Endpoint:

- Peak viral vector levels (vg/ml) post fordadistrogene movaparvovec administration for each of the five profiles – one without MNase treatment for whole blood, one without MNase for saliva, one with MNase for saliva, one without MNase for urine, one with MNase for urine

Analysis:

- Analysis set: Viral Vector Shedding subset of Safety Analysis Set (through Week 52) ([Section 4](#)).
- Analysis methodology: Not applicable.
- Missing data: Missing/undetectable results will not be imputed.
- N, mean, SD, median, Q1, Q3, minimum, and maximum will be provided .

Endpoint:

- Time in weeks of peak viral vector shedding post fordadistrogene movaparvovec administration for each of the five profiles – one without MNase treatment for whole blood, one without MNase for saliva, one with MNase for saliva, one without MNase for urine, one with MNase for urine

Analysis:

- Analysis set: Viral Vector Shedding subset of Safety Analysis Set (through Week 52) ([Section 4](#)).
- Analysis methodology: Not applicable.
- Missing data: Missing/undetectable results will not be imputed.
- N, mean, SD, median, Q1, Q3, minimum, and maximum will be provided.

Endpoint:

- Time in weeks to undetectable viral vector (time to clearance of viral vector) from date of fordadistrogene movaparvovec administration for each of the five profiles – one without MNase treatment for whole blood, one without MNase for saliva, one with MNase for saliva, one without MNase for urine, one with MNase for urine.
- Time in weeks to the last undetectable viral vector from date of fordadistrogene movaparvovec administration for each of the five profiles – one for whole blood, two for saliva, two for urine.

Analysis:

- Analysis set: Viral Vector Shedding subset of Safety Analysis Set (through Week 52) ([Section 4](#)).

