	Week 1, Day 4	4	4	5
	Week 1, Day 6	6	6	6
	Week 1, Day 7	7	7	7
	Week 2, Day 8	8	8	8
	Week 2, Day 9	9	9	9
	Week 2, Day 10	10	10	12
	Week 2, Day 14	14	13	17
	Week 3	21	18	27
	Week 5	34	28	47
	Week 9	60	48	75
	Week 13	90	76	105
	Week 18	120	106	180
	Week 35	240	181	300
		Week 52	360	301
ECGs ^b	Week 1 Day 1	1	1	2
	Week 1, Day 7	7	3	9
	Week 2, Day 14	14	10	17
	Week 3	21	18	27
	Week 5	34	28	47
	Week 9	60	48	75
	Week 13	90	76	105
	Week 18	120	106	180
	Week 35	240	181	300
	Week 52	360	301	390

a: If multiple values are observed within a window, the average of all those values will be used.

b: For quantitative values, if multiple values are observed within a window, the average of all those values will be used. For qualitative values, if multiple visits are windowed, the abnormality flag will be used in generating the incidence of abnormality.

The below analysis windows will be used for viral vector shedding. If multiple values are observed within a window, the largest value will be included in the analysis.

Parameter	Visit label	Target day ¹	Window lower limit	Window upper limit
Viral vector shedding (Whole blood)	Week 1, Day 2	2	2	2
	Week 1, Day 4	4	3	11
	Week 3	21	12	40
	Week 9	60	41	75

Parameter	Visit label	Target day ¹	Window lower limit	Window upper limit
	Week 13	90	76	105
	Week 18	120	106	180
	Week 35	240	181	300
	Week 52	360	301	390
Viral vector shedding (urine and saliva)	Week 1, Day 1	1	1	1
	Week 1, Day 2	2	2	2
	Week 1, Day 4	4	3	5
	Week 1, Day 7	7	6	8
	Week 2, Day 10	10	9	11
	Week 2, Day 14	14	12	16
	Week 3	21	17	25
	Week 5	34	26	47
	Week 9	60	48	75
	Week 13	90	76	105
	Week 18	120	106	180
	Week 35	240	181	300
	Week 52	360	301	390
1. Relative to Day 1 (day of IP administration) 2. If Year 2 Day 1 IP is administered after Day 390, the upper limit for the Week 52 window will be Day 390. If Year 2 Day 1 IP is administered on or prior to Day 390, the upper limit for the Week 52 window will be one day before the day of Year 2 Day 1 IP administration.				

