		Based on protocol amendment 5	Section 2.2.3 
 Modified the text to align with the protocol
		SAP content clarification	Section 3.2 
 Add an imputation approach for mini-dystrophin expression levels below the limit of quantification Clarified the conversion of local laboratory and central laboratory CK values to standard units
		Based on protocol amendment 5	Section 3.3.1 
 Updated details on the spirometry testing process per the protocol
		Based on protocol amendment 5	Section 3.3.3 and Section 6.3.7 
 Added details on sample collection in Japan Changed DNase to MNase
		SAP content clarification	Section 3.4.2 Clarified DMD diagnoses of interest
		SAP content clarification	Section 3.5 
 Added details on the vital signs baseline definition
		Based on protocol amendment 5	Section 3.5.2 
 Updated Table 2 per the protocol Clarified the conversion of local laboratory and central laboratory values to standard units
		Based on protocol amendment 5	Section 3.5.3 
 Added protocol text regarding the collection period for non-serious and serious AEs that are to be recorded on the AE CRF
		SAP content clarification	Section 4 
 Modified the Viral Vector Shedding population to require at least 2 post-Baseline measurements within first 7 days after fordadistrogene movaparvovec administration to ensure adequate data is collected to determine peak levels

		Based on protocol amendment 5	Section 5 
 Modified description/justification of IAs to align with the protocol
		New analysis	Section 6.4 
 Added subset analyses based on Screening age strata
		SAP content clarification	Section 6.6.1 
 Added a summary of treatment-related serious TEAEs
		SAP content clarification	Section 6.6.2 
 Clarified graphical displays for CK and GLDH
		SAP content clarification	Section 6.6.3 
 Clarified how multiple records at a particular timepoint will be handled
		Based on protocol amendment 5	Section 7 
 Modified description/justification of IAs to align with protocol

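### An early-sampling condition recorded as serving peak levels also decides who enters the whole-blood clearance analysis, which does not need it

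*SAP*

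**What the plan says.** Section 4 defines one Viral Vector Shedding population, applied matrix by matrix. A participant must have received active treatment on Day 1 and be one "who had at least two post-Baseline measurements within the first 7 days after fordadistrogene movaparvovec administration".

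Section 6.3.8 names this population for every shedding endpoint in the same words: "Analysis set: Viral Vector Shedding subset of Safety Analysis Set (through Week 52"). That covers peak level, time of peak, "Time in weeks to undetectable viral vector (time to clearance of viral vector) from date of fordadistrogene movaparvovec administration", and time to the last undetectable result. The last two are summarised by Kaplan-Meier.

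Section 3.3.4 defines time to undetectable as running from dosing "to the first of the 2 consecutive negative results identified". Time to last undetectable runs to the second of that pair. If clearance is not confirmed, the time is censored at the last sample in that matrix. Neither definition asks for a minimum number of early samples.

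Current section 4 gives no reason for the condition. The version 4 entry in Appendix 6 does: "to ensure adequate data is collected to determine peak levels". It is cited here only as the recorded rationale for a condition still in force.

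**The concern.** A condition that secures enough early data to find a peak is reasonable for peak level and time of peak. The clearance endpoints ask a different question, namely when two consecutive negatives first appear. A boy with one early blood sample and every later sample through confirmed clearance has a fully observed clearance time, yet the condition removes him.

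This bites in whole blood, where the number of samples planned for the first 7 days equals the number required. At stake is the precision of a descriptive curve built on a small subset: section 3.3.4 plans sampling in about 30 actively treated boys.

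**Working it through.** The SAP gives no figure for this point, so there is nothing to reproduce. The check counts planned samples and then translates an assumed failure rate into a loss.

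**Planned samples in the first 7 days (Appendix 2.1 shedding windows)**
- Whole blood: target Days 2 and 4, then Day 21. Two planned, two required, none spare.
- Urine and saliva: target Days 1, 2, 4 and 7. Four planned, two required, two spare. This counts the Day 1 sample as post-dose.

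**Inputs**
- N = about 30 actively treated boys sampled (section 3.3.4).
- m = probability that a given early sample is missed or falls outside the 7-day limit. The SAP gives no value. It is assumed equal and independent across samples, with no unscheduled sample to fill a gap.

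**Formulas**
- Whole blood, excluded: 1 − (1 − m)².
- Urine or saliva, excluded (fewer than 2 of 4 obtained): m⁴ + 4m³(1 − m).
- Standard error ratio, taking the standard error as proportional to 1/√n: √(30 / (30 − boys lost)).

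**Results**

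| m (assumed) | Whole blood excluded | Boys lost of 30 | Standard error ratio, whole blood | Boys lost of 30, urine or saliva |
|---|---|---|---|---|
| 2% | 1 − 0.98² = 3.96% | 1.2 | √(30/28.8) = 1.02 | 0.00 |
| 5% | 1 − 0.95² = 9.75% | 2.9 | √(30/27.1) = 1.05 | 0.01 |
| 10% | 1 − 0.90² = 19.0% | 5.7 | √(30/24.3) = 1.11 | 0.11 |

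The 10% row is a stress case. Section 3.5.3 refers to a 7-day hospitalization after dosing, and Table 2 schedules laboratory draws on Days 2, 4 and 6 to 10. Both make missed or delayed early blood samples less likely, so 2% to 5% is the more credible range.

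**What counts as too late.** A Day 2 sample drawn on Day 3, or a Day 4 sample drawn on Days 5 to 7, still counts. Only a missed sample, or one after the limit, excludes a boy. The SAP does not say whether the period ends on Day 7 or Day 8 when Day 1 is the dosing day.

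**The case against.** The best defence is that a single evaluable set per matrix keeps one N across four descriptive endpoints. The objective is exploratory, limited to Cohort 1 and carries no hypothesis test. The rationale comes from a version 4 log entry, the population description was revised again in version 5, and current section 4 does not say that the condition serves the peak alone. All of this is fair, and it limits the importance of the point. It does not supply a reason for clearance to need the condition, and no other reason is recorded.

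It can also be said that early samples inform clearance if blood is already negative by Day 2 or Day 4, and the SAP does not say when clearance is expected. In that case a boy with a gap would have his first negative recorded later than it occurred. His later results or a censored time would still be usable, so excluding him is not the remedy.

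Three stronger readings are tempting but not supported:
- **That the condition contradicts the visit windows.** In Appendix 2.1 the whole-blood Day 4 row reads "Week 1, Day 4 4 3 11", so a Day 9 sample carries the Day 4 label but fails the 7-day condition. The window assigns a visit label, while the population condition counts actual days. None of the four endpoints in section 3.3.4 is defined by visit label. The two rules do different jobs and can stand together.
- **That a sizeable share of boys will be lost.** No missed-sample rate is given, and the hospitalization points to a low one.
- **That the clearance estimate is biased.** That would need early missingness to be related to clearance, and nothing in the SAP shows it. What can be shown is a possible loss of precision.

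**Conclusion.** The point holds as a minor one. Section 6.3.8 applies to the two time-to-undetectable endpoints a condition whose only recorded purpose is peak levels. In whole blood there is no spare planned sample to absorb a gap.

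The exclusion is per matrix: a boy dropped for whole blood stays in the urine and saliva analyses if he meets the condition there. The expected cost is about 1 to 3 of 30 boys and a 2% to 5% larger standard error for the whole-blood clearance curve. This rests on an assumed 2% to 5% failure probability per early sample, independence between samples, and no unscheduled early samples. Urine and saliva are hardly affected.

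**What to change.** Keep the two-samples-in-7-days condition, as written, for peak level and time of peak. It should not be loosened to accept whole-blood samples up to Day 11: that would admit boys with a long early gap and weaken the coverage that the peak needs.

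For time to undetectable and time to last undetectable, define the set in each matrix as all participants dosed with active treatment on Day 1 who have post-dose shedding results in that matrix. Siblings and those meeting exclusion criterion 15 stay included as now, and the censoring rules of section 3.3.4 apply unchanged. A boy with very few samples will mostly be censored and add little, but he need not be removed.

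The change touches the population table in section 4, the analysis-set lines in section 6.3.8 and the matching rows of Appendix 1. It needs no new samples or assays. The price is a second N per matrix in the tables. It should be made before the population classification that section 4 places ahead of unblinding, so that it cannot look like a choice made after seeing results.
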